3.6 Coronavirus Disease 2019

In March, 2020, the emerging coronavirus disease 2019 (COVID-19) pandemic resulted in implementation of urgent safety measures designed to ensure subject safety. Mechanisms to record information on the potential impact of the COVID-19 pandemic on data itself, as well as data collection and integrity, were implemented (as detailed in the “Guidance for Site Documentation and Data Management Querying of Data Impacted by COVID-19” [GSD] in the Data Management Plan).

The impact of COVID-19 on the statistical analysis is discussed in each of the relevant sections of this SAP.

Subjects who remained in this study who could not attend clinic visits were allowed to participate in remote visits via telephone or video, or site staff conducted the visit in a subject’s home. Sites were required to document details of all visits that are administered remotely.

4 ANALYSIS SETS

Safety Analysis Set

The Safety Analysis Set includes all randomized subjects who received at least one dose of study drug (ACP-044 or placebo). Subjects will be analyzed based on the treatment that they actually received. The Safety Analysis Set will be used for all safety analyses.

Full Analysis Set

The Full Analysis Set includes all randomized subjects who received at least one dose of study drug and with baseline pain assessments and at least one post-baseline pain assessment. The Full Analysis Set will be used for the analysis of all efficacy endpoints. Subjects will be analyzed based on their randomized treatment assignment.

Pharmacokinetics Analysis Set

The Pharmacokinetics Analysis Set includes all subjects with at least one measurable ACP-044 plasma concentration. The Pharmacokinetics Analysis Set will be used for ACP-044 plasma concentration summaries.

5 DATA HANDLING CONVENTIONS

All data collected in the study will be listed.

5.1 General Data Reporting Conventions

Continuous variables will be summarized using the following descriptive statistics: number of subjects, mean, median, standard deviation (SD), standard error (SE), minimum, maximum and quartiles when necessary. Unless specified otherwise, means, medians, and confidence intervals (CIs) will be presented to one more decimal place than the raw data, and the standard deviations and standard errors will be presented to two more decimal places than the raw data. In general, the maximum number of decimal places is 4 and values will be truncated to 4 decimal places in situations where there are more than 4 decimal places.

Wherever possible data will be decimal aligned.

Categorical variables will be summarized by the number of subjects and the percent of subjects in each category; the number of subjects and the percentage of subjects with missing data will be summarized for demographic and baseline characteristics (if applicable).

Categories with zero counts will not have zero percentages displayed. For demographic summaries, percentages will be calculated by using the total number of subjects in the given treatment group as the denominator. Percentages will be presented with one decimal place.

Duration in months will be calculated as ([the number of days / 365.25] *12).

Unless specified otherwise, all statistical tests will be 2-sided hypothesis tests performed at the significance level of 5% for main effects and all CIs will be 2-sided 95% CIs. P-values will generally be presented to 4 decimal places; values less than 0.0001 will be presented as <0.0001.

Values that are collected with “<” or “>” signs will generally be analyzed as the numerical value without the sign in tables and figures. In listings, these data will be reported as collected with the sign.

5.2 Derived Variables

In general, the assessment scale scores will be directly taken from the electronic case report form (eCRF).

5.2.1 Numeric Rating Scale (NRS) of Pain Intensity Scores

A 0 to 10 NRS will be used to assess the subject’s pain throughout the study. Subjects will be required to assess and record daily in the eDiary their knee pain intensity and daily use of rescue medication. Subjects will be rating both the average daily pain as well as their worst daily pain.

Knee pain intensity will be assessed by describing their knee pain at the present time from 0 to 10 where “0” means “no pain at all” and “10” means “the worst pain imaginable”.

Pain intensity assessments are to be recorded in the evening prior to their 4th dose of the day.

Subjects are encouraged to refrain from acetaminophen use for at least 24 hours prior to the start of study visits in order to minimize the confounding effects of the rescue medication on efficacy measurements. At study visits, pain assessments should be performed before blood sample collection, ECG, and other procedures

5.2.2 Patient Global Impression of Change (PGIC)

The self-report measure Patient Global Impression of Change (PGIC) reflects a subject’s belief about how their pain has changed since start of study treatment. PGIC is a 7-point scale depicting a subject’s rating of overall improvement. Subjects rate their change as “very much improved” = 1, “much improved” = 2 “minimally improved” = 3 “no change” = 4 “minimally worse” = 5 “much worse” = 6 or “very much worse” = 7.

The PGIC will be completed at Week 1, Week 2, and Week 4 (EOT)/ET. At study visits, the PGIC should be performed before blood sample collection, ECG, and other procedures.

5.2.3 Western Ontario and McMaster Universities Osteoarthritis Index (WOMAC)

The WOMAC is widely used in the evaluation of hip and knee osteoarthritis (Collins et al. 2011) and rates pain during the last 48 hours. It is a self-administered questionnaire consisting of 24 items divided into three subscales:

- Pain (5 items): during walking, using stairs, in bed, sitting or lying, and standing upright
- Stiffness (2 items): after first waking and later in the day
- Physical Function (17 items): using stairs, rising from sitting, standing, bending, walking, getting in/out of a car, shopping, putting on/taking off socks, rising from bed, lying in bed, getting in/out of bath, sitting, getting on/off toilet, heavy domestic duties, light domestic duties

The test questions are scored on a scale of 0-4, which correspond to: None (0), Mild (1), Moderate (2), Severe (3), and Extreme (4). The scores for each subscale are summed up, with a possible score range of 0-20 for Pain, 0-8 for Stiffness, and 0-68 for Physical Function. The sum of the scores for all three subscales provides the total WOMAC score. Higher scores on the WOMAC indicate worse pain, stiffness, and functional limitations.

The WOMAC will be completed at Baseline (Week 0), Week 1, Week 2, and Week 4 (EOT)/ET. At study visits, the WOMAC should be performed before blood sample collection, ECG, and other procedures.

5.2.4 Brief Pain Inventory – Short Form (BPI-sf)

The BPI is a self-report measure used to assess the severity of pain and its impact on functioning in subjects with chronic diseases. The short form version uses a 24-hour recall period (i.e., assesses pain and its impact over the previous 24 hours).

The BPI uses a 0 (no pain) to 10 (pain as bad as you can imagine) numeric rating scale to measure how much pain has interfered with seven daily activities, including general activity, walking, work, mood, enjoyment of life, relations with others, and sleep.

The BPI will be completed at Baseline (Week 0), Week 1, Week 2, and Week 4 (EOT)/ET. At study visits, the BPI should be performed before blood sample collection, ECG, and other procedures.

5.2.5 12-item Short Form Survey (SF-12)

The SF-12 survey, version 2 (SF-12v2), is a shortened form (12 items) of the SF-36 Health Survey (Ware et al. 1996). It is a self-reported general assessment of health-related quality of life from the subject's perspective. The SF-12 has eight domains including physical health

summary measures: physical functioning, role-physical, bodily pain, and general health and mental health summary measures: vitality, social functioning, role-emotional, and mental health. From the evaluation of these domains, algorithms are used to generate physical and mental health composite summary scores, PCS and MCS, respectively, for comparison to normative data. In normative data, the mean score is set to 50; thus, scores >50 indicate better physical or mental health than the mean scores and scores <50 indicate worse health. The timeframe for this scale is the past 4 weeks.

Scales of SF-12 (health survey) Physical Component Summary (PCS) and Mental Component Summary (MCS) will be derived using the weights provided in the SF-12 manual developed by J. Ware, M. Kosinski and S. Keller.

For variable 12 (Physical Component Summary (PCS) and Mental Component Summary (MCS) of SF-12), PCS and MCS are created from the SF-12 survey in this way. First, subjects with missing answer to any one of the 12 items will be ignored, i.e., will have their PCS-12 and MCS-12 scores missing. Indicator variables (1/0) will be created for all choices of each the 12 items, except that the choice associated with the best health status under each item. Thus totally 35 indicator variables will be created. For example, for item “In general, would you say your health is”, indicator variables will be created for each of the choices “Poor”, “Fair”, “Good”, and “Very Good”, but not the choice “Excellent”. This means that if a subject marks “Good” under this item, the indicator variable for “Good” will have a value 1, and the indicator variables for “Poor”, “Fair” and “Very Good” will have value 0. If a subject marks “Excellent” for this item, all indicator variables under this item will have value 0. Then all these indicator variables will be weighted based on the SF-12 Manual for the PCS-12 and MCS-12 separately. Summing of these indicator variables based on their weight, and plus the constant (56.57706 for PCS-12 and 60.75781 for MCS-12) will provide the PCS-12 and MCS-12 scores for each subject.

The SF-12 will be completed at Baseline (Week 0) and Week 4 (EOT)/ET.

5.2.6 Hospital Anxiety and Depression Scale (HADS)

The HADS was developed to detect states of anxiety or depression ([Zigmond and Snaith 1983](#)). The questionnaire focuses on non-physical symptoms so that it can be used to diagnose depression in people with significant physical ill-health. The questionnaire comprises seven questions for anxiety and seven questions for depression, which are each scored separately. Each item on the questionnaire is scored from 0 (No, not at all) to 3 (Yes definitely), for a total score between 0 to 21 for either anxiety or depression. The timeframe for this scale is the past week.

The HADS will be completed at Screening, Baseline (Week 0), and Week 4 (EOT)/ET.

5.2.7 Columbia-Suicide Severity Rating Scale (C-SSRS)

The C-SSRS is assessed at Baseline, Day 7, Day 14, and Day 28 (EOT/ET).

The C-SSRS version assessing information since the last visit will be completed at all visits (including the Baseline visit).

There are 5 questions about suicidal ideation, representing 5 types of suicidal ideation: wish to be dead; non-specific active suicidal thoughts; active suicidal ideation with any methods (not plan) without intent to act; active suicidal ideation with some intent to act, without specific plan; active suicidal ideation with specific plan and intent. If a subject answers “yes” to any of these 5 questions, this subject will be counted as having suicidal ideation.

There are 5 questions about suicidal behavior, representing 5 types of suicidal behavior: preparatory acts or behavior; aborted attempt; interrupted attempt; actual attempt; suicide. If a subject answers “yes” to any of these 5 questions, this subject will be counted as having suicidal behavior.

Suicidality is defined as a subject who reported at least 1 occurrence of suicidal ideation or at least 1 occurrence of suicidal behavior at any post-Baseline visit including unscheduled and out of window visits.

Missing C-SSRS item scores will not be imputed.

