 - a. Systolic blood pressure ≥ 180 mmHg or diastolic blood pressure ≥ 100 mmHg at Screening or Baseline

- b. Systolic blood pressure of 160-179 mmHg or diastolic blood pressure of 100-109 mmHg at Screening or Baseline, AND a history of end-organ damage (including history of left ventricular hypertrophy, heart failure, angina, myocardial infarction, stroke, transient ischemic attack, renal failure, peripheral arterial disease and moderate to advanced retinopathy [hemorrhages or exudates, papilledema])
- c. Known clinical diagnosis of orthostatic hypotension
- d. Evidence of orthostatic hypotension at Baseline, defined as a decrease in systolic blood pressure ≥ 20 mmHg or diastolic blood pressure ≥ 10 mmHg after transitioning from the supine position (after resting for 5 minutes) to standing at 1 or 3 minutes. Subjects unable to stand may be assessed while sitting upright.

18. Congestive heart failure with New York Heart Classification of stage III or IV
([Appendix A](#))

19. Transient ischemic attack or cerebrovascular accident within the past 12 months prior to Screening, or myocardial infarction, or acute coronary syndromes within the past 6 months prior to Screening

20. Is suicidal at Screening or Day -1 as defined below:

- a. An answer of “yes” to C-SSRS questions 4 or 5 (current or over the last 6 months); OR
- b. Has attempted suicide within 1 year prior to Screening; OR
- c. Is actively suicidal in the Investigator’s judgment

21. Beck Depression Inventory-II (BDI-II) score ≥ 29 at Screening

22. Has a history of uncontrolled diabetes mellitus (DM), Type 1 or Type 2 DM, or glycosylated hemoglobin (HbA_{1c}) $> 8.0\%$ at Screening

23. Known history of human immunodeficiency virus (HIV) infection

24. Known history of infection with hepatitis B virus. Subjects with a history of hepatitis B are eligible if there is documentation of a negative test for hepatitis B surface antigen and a positive test for antibodies to the hepatitis B virus surface antigen

25. Known history of infection with the hepatitis C virus. Subjects with a history of hepatitis C are eligible if there is documentation of a negative hepatitis C virus RNA test

26. Has a known or suspected history of drug abuse or a recent (within the last 5 years) history of alcohol abuse

27. Use of medicinal or recreational marijuana or cannabidiol (CBD) within 1 month prior to Screening. The use of these substances are not allowed throughout the study

Other Criteria

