6.5.4 Columbia-Suicide Severity Rating Scale

The C-SSRS monitors changes in suicidal thinking and behavior over time, in order to determine risk ([Posner et al. 2011](#)). The following four constructs are measured: the severity of ideation, the intensity of ideation, behavior, and lethality.

The Baseline/Screening version will be administered at Screening, and the Since Last Visit version will be administered at all subsequent visits. The C-SSRS results for each subject should be reviewed by the Investigator after completion. If at any time the C-SSRS results for a given subject reveal potential suicidality, then the Investigator should assess the clinical significance of such results. If a clinically significant risk of suicidality is identified for a subject, then the Investigator should discontinue the subject and implement appropriate treatment ([Section 4.5](#)).

C-SSRS will be completed at all designated study visits.

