14.6 Other Safety Variables

14.6.1 Suicidality Based on C-SSRS

The event counts and the number and percentage of subjects reporting any post Baseline suicidal ideation, suicidal behavior, or suicidality will be tabulated by treatment group. The event counts and the number and percentage of subjects reporting any post-Baseline non-suicidal self-injurious behavior will also be tabulated. For calculating the percentages, the denominator will be the number of subjects in the Safety Analysis Set.

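### The C-SSRS suicidality table has no pre-treatment comparison, so entry ideation that persists or recurs on treatment is counted the same as new ideation

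*SAP*

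**What the plan says.** **Counting rule.** SAP 5.2.7 lists five types of ideation. After a yes to any of them, "this subject will be counted as having suicidal ideation"; behavior has a parallel rule. Suicidality is then "at least 1 occurrence of suicidal ideation or at least 1 occurrence of suicidal behavior at any post-Baseline visit", unscheduled and out-of-window visits included. SAP 14.6.1 plans counts and percentages of subjects "reporting any post Baseline suicidal ideation, suicidal behavior, or suicidality will be tabulated by treatment group", and the same for non-suicidal self-injury, with the Safety Analysis Set as denominator. Neither section mentions the pre-treatment state.

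**Eligibility.** Protocol 4.2, criterion 20a, excludes on "C-SSRS questions 4 or 5 (current or over the last 6 months"). Parts b and c add a suicide attempt within a year and the investigator's judgment that the subject is actively suicidal. A yes to questions 1 to 3 is not in itself a reason for exclusion.

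**Visits and forms.** SAP 5.2.7 says "The C-SSRS is assessed at Baseline, Day 7, Day 14, and Day 28 (EOT/ET") and, on the form, "The C-SSRS version assessing information since the last visit will be completed at all visits (including the Baseline visit"). Protocol 6.5.4 says "The Baseline/Screening version will be administered at Screening, and the Since Last Visit version will be administered at all subsequent visits". Protocol Table S-1 and SAP Appendix A mark the scale at Screening, Visit 2, Week 0, Weeks 1, 2 and 4, and unscheduled visits.

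**The concern.** The C-SSRS is a named safety endpoint (Protocol 2.4.1). Its table should help a reader judge whether suicidal ideation appears or worsens on ACP-044. A count of any yes after Baseline mixes two groups: subjects whose ideation began or worsened on treatment, and subjects who entered with milder ideation that continued or came back.

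The other main safety summaries in the SAP do compare with the pre-treatment state:

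- Treatment-emergent events must start after the first dose (14.1).
- Laboratory values get changes from Baseline and shift tables (14.2).
- The observed-value criteria for vital signs also require a change from Baseline (Table 4).
- ECGs get change and shift summaries (14.4).

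SAP section 19 cuts back only the efficacy analyses, so the C-SSRS table is still to be produced. In arms this small, one subject whose ideation was already present can look like a signal, or can make a new case in another arm harder to see.

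**Working it through.** The plan gives no figure to reproduce here. The check compares the texts and adds a short illustration.

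**1. What the planned rule counts.** The post-Baseline forms ask only about the time since the previous visit, and Protocol 3.1.3 puts the first dose after all Baseline assessments. The five cases below follow. The last two columns apply the two references proposed in the fix.

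| Subject | Planned count | New or worse than worst pre-treatment | New or worse than Visit 2 and Week 0 |
|---|---|---|---|
| Type 2 before dosing, none after | no | no | no |
| Type 2 at Screening, Visit 2 and Week 0; type 2 after dosing | yes | no | no |
| Type 1 before dosing, type 3 after | yes | yes | yes |
| None before dosing, type 1 after | yes | yes | yes |
| Type 2 five months before Screening, none at Visit 2 or Week 0; type 2 after dosing | yes | no | yes |

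The planned count cannot tell rows 2 to 5 apart. Row 1 shows that entry ideation which does not return is never counted.

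**2. Does the general baseline rule help?** SAP 5.5 takes the value closest to, and before, the first dose. For this scale that is the Week 0 form, which looks back to Visit 2, about 7 to 10 days (a 7-day period plus the 3-day window). Against the 6 months in criterion 20a, that is 7/182.6 = 3.8% to 10/182.6 = 5.5%. It is genuine pre-treatment information with a short reach, and neither 5.2.7 nor 14.6.1 uses it.

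**3. Visits and forms side by side.** For the four visits in SAP 5.2.7 (Baseline, Days 7, 14 and 28), the Since Last Visit form is what Protocol 6.5.4 requires. What is missing is the Screening assessment with its Baseline/Screening form, and Visit 2. Adding both to 5.2.7 would leave every count in 14.6.1 unchanged, because that table uses post-Baseline visits only.

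**4. Size of one subject.** SAP section 1 gives 61 randomized, so 61/3 = 20.3 per arm. One subject is 1/20 = 5.0 points, or 1/21 = 4.8 points.

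**5. Illustration under assumptions.** Let p be the share entering with type 1 to 3 ideation and q the share of those who report it again on treatment. The documents give neither. The expected number carried over is 61 × p × q, and the chance of at least one is 1 − (1 − pq)^61.

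| p | q | Expected | Chance of at least one |
|---|---|---|---|
| 1% | 25% | 0.15 | 14% |
| 1% | 100% | 0.61 | 46% |
| 3% | 50% | 0.9 | 60% |
| 5% | 25% | 0.76 | 54% |
| 5% | 100% | 3.05 | 96% |

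With q = 0 there are none. The range is too wide to support any single figure.

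**The case against.** Four things can be said for the plan as it stands.

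- **The comparison is already fair.** Incidence after Baseline by randomized arm is a coherent comparison, since entry ideation is balanced on average. This is true in expectation. With about 20 per arm, chance imbalance remains, though that applies to every descriptive safety count in this trial.
- **The data are available.** Screening, Visit 2 and predose Week 0 assessments are collected, and SAP section 5 lists all collected data. With few positive subjects, a reader can look up each one. This stands, and it is the main reason why the impact is low.
- **The documents promise no emergent or shift table for this scale.** Correct. The change is an improvement and does not restore a broken commitment.
- **A worst-over-6-months reference can hide a true recurrence**, as in row 5 above. This also stands, so the fix shows a recent reference as well and keeps the planned count.

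A reader might infer something stronger: that the omissions in SAP 5.2.7 leave the trial without a valid pre-treatment reference, so that ideation brought into the trial is reported as post-Baseline suicidality. The documents do not support this. Using the Since Last Visit form at Week 0 follows Protocol 6.5.4. Pre-dose data exist and are listed. Only ideation that persists or recurs on treatment is counted, and this comes from the any-post-Baseline definition, not from the visit list.

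**Conclusion.** Two separate points hold. First, the suicidality table cannot separate ideation that persists or recurs from ideation that is new or worse, because no pre-treatment comparison is planned. Each subject affected moves an arm by about 5 percentage points. How many there would be is unknown; the 14% to 96% range for at least one rests wholly on assumed prevalence and recurrence, and on all 61 being in the Safety Analysis Set. Second, SAP 5.2.7 is incomplete on visits and forms against Protocol 6.5.4 and the SAP's own Appendix A; this has no effect on the table by itself.

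This is a cheap improvement with low impact. The table is descriptive, Protocol 9.5.5 plans no formal safety testing, the trial stopped at 61 subjects, and the investigator's review of each C-SSRS does not depend on this table.

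**What to change.** 1. **SAP 5.2.7:** match visits and forms to Protocol 6.5.4 and Appendix A. That means the Baseline/Screening form at Screening, and the Since Last Visit form at Visit 2, predose Week 0, Weeks 1, 2 and 4 or early termination, and unscheduled visits.
2. **SAP 5.2.7:** define the pre-treatment reference for this scale, in place of the general rule in 5.5, as the most severe ideation type and any behavior over the Screening look-back, Visit 2 and predose Week 0. Define a second, recent reference from Visit 2 and predose Week 0 only.
3. **SAP 14.6.1:** add a pre-treatment C-SSRS summary by arm. Add rows for ideation or behavior that is new or more severe than each reference, and keep the any-post-Baseline count beside them.

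The cost is SAP wording and a few table rows, with no new data or procedures. The emergent counts will be equal to or lower than the planned count, so all of them should be shown together.
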